5.3. Lifestyle Considerations

Partners (male and female) of subjects should use effective methods of contraception.

5.4. Screen Failures

A screen failure occurs when a subject who consents to participate in the study is not subsequently entered in the study. A minimal set of screen failure information is required to ensure transparent reporting of screen failure subjects to meet the Consolidated Standards of Reporting Trials (CONSORT) publishing requirements and to respond to queries from regulatory authorities. Minimal information includes demography, screen failure details, eligibility criteria, and any serious adverse event (SAE).

Individuals who do not meet the criteria for participation in this study (screen failure) may be rescreened after discussion with Medical Monitor. Rescreened subjects should be assigned a new subject number.

6. Study Treatment and Concomitant Therapy

6.1. Study Treatment Administered

E-602 is supplied as a sterile solution for IV infusion in glass vials. Each container is filled with 10 mL solution which contains 100 mg E-602 active ingredient in 20 mM glutamic acid-sodium hydroxide buffer with 8% (w/v) sucrose and 0.04% (w/v) polysorbate 80 at a pH value of 4.7. Cemiplimab is provided as a sterile solution (350 mg/7 ml vial) for IV infusion.

Protocol Number: PAL-E602-001

Version 8.0, 24 August 2023

For all subjects treated in the study, E-602 will be administered via IV infusion once a week at the assigned doses summarized below. For the combination therapy cohorts, 350 mg of cemiplimab will be administered via IV infusion once every 3 weeks. Subjects receiving ≥10 mg/kg of E-602 as monotherapy or in combination with cemiplimab should receive premedication including antihistamines and acetaminophen as indicated in the Pharmacy Manual. Corticosteroids should be used as premedication for subjects with previous infusion reaction(s) to E-602 as indicated in the Pharmacy Manual (see Pharmacy Manual, Section 10.5). All procedures and assessments must be completed prior to the start of dosing.

In each 21-day cycle, E-602 will be administered on Days 1, 8, and 15, and cemiplimab will be administered on Day 1. When the cemiplimab combination will be administered, cemiplimab should be administered first and E-602 administered at least 30 minutes after the cemiplimab infusion is completed. No intrasubject dose escalation of E-602 will be permitted. Details of study treatment administration methods will be provided in the Pharmacy Manual.

Cemiplimab should be administered in compliance with the manufacturer's labeling information (Libtayo® Prescribing Information 2022).

Phase 1 Treatment (Planned):

Five escalating dose cohorts of E-602 monotherapy and 2 escalating dose cohorts of combination therapy will be treated.

Cohort	Number of Subjects ^a	Dose of E-602	Frequency of E- 602	Dose of Cemiplimab	Frequency of Cemiplimab
101	3 – 6	1 mg/kg	once a week	n/a	n/a
102	3 – 6	3 mg/kg	once a week	n/a	n/a
103	3 – 6	10 mg/kg	once a week	n/a	n/a
104	3 – 6	20 mg/kg	once a week	n/a	n/a
105	3 – 6	30 mg/kg	once a week	n/a	n/a
111	3 – 6	20 mg/kg	once a week	350 mg	once every 3 weeks
112	3 – 6	to be determined	once a week	350 mg	once every 3 weeks

^a Phase 1 cohorts may be backfilled to a maximum of 15 subjects.

The dose for E-602 in the combination therapy cohorts will be initiated at dose level(s) that have previously completed dosing and DLT assessments (Cycle 1) as monotherapy.

Dose modifications will be made according to Section 6.5.

Phase 2 Treatment (Planned):

Subjects in Phase 2 will receive the following treatment:

Cohort	Number of Subjects	Advanced Disease	Dose of E-602	Frequency of E-602	Dose of Cemiplimab	Frequency of Cemiplimab
201	16 – 31	melanoma	monotherapy RP2D	once a week	n/a	n/a
202	16 – 31	NSCLC	monotherapy RP2D	once a week	n/a	n/a
203	16 – 31	TBDa	monotherapy RP2D	once a week	n/a	n/a
211	16 – 31	melanoma	combination RP2D	once a week	350 mg	once every 3 weeks
212	16 – 31	NSCLC	combination RP2D	once a week	350 mg	once every 3 weeks
213	16 – 31	TBDa	combination RP2D	once a week	350 mg	once every 3 weeks

^a The third cohort will treat subjects with one of ovarian, colorectal, pancreatic, breast, gastric/EGJ, head and neck or urothelial cancers, based on available data including the Phase 1 results.

The maximum duration of treatment for each subject will be 1 year, regardless of treatment delays. See Section 7.1 for early treatment discontinuation criteria.

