4.1.1. Study Design Overview

Phase 1: Dose Escalation, Monotherapy and Combination Therapy

Phase 1 of the study consists of 5 planned dose escalation cohorts of E-602 as a monotherapy and 2 planned dose escalation cohorts of E-602 in combination with cemiplimab. Phase 1 monotherapy will treat eligible subjects with melanoma, ovarian cancer, non-small cell lung cancer (NSCLC), colorectal cancer, pancreatic cancer, breast cancer, gastric/EGJ cancer, head and neck cancer, or urothelial cancer. Phase 1 combination with cemiplimab will treat eligible subjects with melanoma, NSCLC, gastric/EGJ cancer, head and neck cancer or urothelial carcinoma. The safety of the dose regimens will be evaluated to identify the maximum tolerated dose (MTD) and recommended Phase 2 dose (RP2D) to be used during Phase 2.

The cohorts of E-602 monotherapy will receive E-602 at the doses of 1, 3, 10, 20 and 30 mg/kg, respectively, via intravenous (IV) infusion once a week. Intermediate dosing cohorts may be added in Phase 1. The first subject dosed in a cohort will be a sentinel subject, with at least 24 hours until any subsequent subjects are dosed in the cohort. No intrasubject dose escalation of E-602 will be permitted.

The cohorts of E-602 in combination with cemiplimab will be initiated at dose level(s) that have previously completed DLT assessments (Cycle 1) as monotherapy. Intermediate dosing cohorts may be added in Phase 1. Subjects in the combination cohorts will receive 20 mg/kg E-602 IV once a week (additional dose levels to be determined) and 350 mg cemiplimab IV once every 3 weeks. The first subject dosed in a cohort will be a sentinel subject, with at least 24 hours until any subsequent subjects are dosed in the cohort. No intrasubject dose escalation of E-602 will be permitted.

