9.1. Analysis Sets

DLT Evaluable Set:

Will include all subjects treated in the dose escalation part who have had a DLT within Cycle 1 on study or without a DLT but completed safety assessments through Cycle 1 (3 doses of E-602 administered for monotherapy cohorts and 3 doses of E-602 and 1 dose of cemiplimab administered for combination therapy cohorts). The DLT Evaluable Set will be defined for each dose cohort. Subjects who discontinue prior to completing Cycle 1 (3 doses of E-602 administered for monotherapy cohorts and 3 doses of E-602 and 1 dose of cemiplimab administered for combination therapy cohorts) for reasons other than toxicity may be replaced.

Safety Analysis Set:

Will include all subjects who have received any dose of study treatment. The Safety Analysis Set will be used for safety analyses. Safety Analysis Set may be further defined by the phase of the study, dose, and tumor type.

Efficacy Evaluable Set:

Will include all subjects who receive any dose of study treatment, meet eligibility criteria, have measurable tumor lesions at baseline, and have at least one post-baseline disease assessment per RECIST v1.1. Efficacy Evaluable Set is defined for each cohort in the Phase 2 separately.

Pharmacokinetics (PK) Analysis Set:

Will include all subjects in the Safety Analysis Set for whom adequate data on E-602 plasma concentration are available.

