9.2.5. Efficacy analysis

The primary analysis for efficacy will be based on the cohort-specific efficacy evaluable analysis set. Sensitivity analysis may include pooling additional subjects treated in Phase 1 at the same dose level in the same tumor type.

For objective response rate (ORR), the Clopper-Pearson 80% and 95% confidence intervals (CIs) will be provided. Confidence intervals adjusting for the 2-stage nature of the design may also be provided.

Duration of response (DoR) will be calculated among responders (CR and PR). The Kaplan-Meier method will be used to estimate median DoR and the confidence intervals. Subjects who continue to respond at the time of the analysis will be censored at the last assessment of response.

Progression-free survival (PFS) is measured from the date of first study treatment dose until the first date when progressive disease (PD) is objectively documented or death from any cause. Subjects without PD or death will be censored at the last available tumor assessment. PFS will be summarized using the Kaplan-Meier method.

Overall survival (OS) is measured from the date of first study treatment dose until death. Subjects who are alive will be censored at the last known alive date. OS will be summarized using the Kaplan-Meier method.

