6.3 Efficacy Analyses

The primary efficacy analyses will be based on the efficacy evaluable population. For each tumor indication, subjects administered the same study treatment may be combined for analysis purposes, regardless of study phase. All data from scheduled or unscheduled tumor assessments will be included in the efficacy analyses except for tumor assessments after the initiation of new anti-cancer therapy for the ORR and DoR endpoints as described in Section 4.

Sensitivity efficacy analysis may be performed based on the ITT Population if it is sufficiently different from the efficacy evaluable population and the additional analysis may be informative. Subjects with no measurable baseline disease or no evaluable post-baseline disease assessments (i.e., NE) will be considered non-responders and included in the denominator in the calculation of the ORR for the ITT population.

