8 CHANGES FROM PROTOCOL-SPECIFIED ANALYSIS

There are no changes from the analysis specified in protocol v8.0.

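### Phase 1 subjects whose responses may help select the third Phase 2 tumor type can later be pooled into that type's ORR, which can bias the pooled ORR upward, mainly in cohort 203

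*Protocol*

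**What the plan says.** Protocol 6.1 (footnote to the Phase 2 table) gives the third cohort to one of seven types, the list ending "head and neck or urothelial cancers, based on available data including the Phase 1 results". The synopsis and 4.1.1 say the same. No selection criterion is written. Protocol Section 3 lists confirmed ORR as a Phase 1 secondary endpoint, so response is among the Phase 1 results.

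On analysis, Protocol 9.2.5 states: "The primary analysis for efficacy will be based on the cohort-specific efficacy evaluable analysis set". Protocol 9.1 adds: "Efficacy Evaluable Set is defined for each cohort in the Phase 2 separately". Pooling appears only as an option: "Sensitivity analysis may include pooling additional subjects treated in Phase 1 at the same dose level in the same tumor type".

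The SAP is looser. Sections 6.1 and 6.3 both say: "For each tumor indication, subjects administered the same study treatment may be combined for analysis purposes, regardless of study phase". That sentence carries no sensitivity label, and SAP Section 3 defines study treatment as monotherapy or combination without reference to dose. SAP 3.3 does not tie the efficacy evaluable population to the individual Phase 2 cohort. SAP Section 8 nevertheless declares: "There are no changes from the analysis specified in protocol v8.0".

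The only interval adjustment either document mentions is for the two-stage design. Nothing addresses selection of the tumor type.

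**The concern.** If the third type is picked partly because its Phase 1 subjects responded well, their response rate is on average above the type's true rate: the best of several small samples is partly luck. Adding those subjects to the Phase 2 cohort carries the luck into the ORR. Labelling the analysis as sensitivity does not remove this. Restricting it to the same dose does not either, if responses at that dose helped drive the choice.

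At stake is how the pooled ORR of cohort 203, and to a lesser extent 213, is read. A borderline Phase 2 result could look better after pooling, and the Clopper-Pearson interval would not reflect the selection. Melanoma and NSCLC do not have this problem, because they were not chosen on Phase 1 results.

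**Working it through.** **The plan's own figure.** Protocol 9.4 and SAP 2.3: 16 subjects, continue if at least 2 respond, 31 in total, promising if at least 6 respond, null 10%, alternative 25%. The probability of a promising result is the sum over x ≥ 2 of P(X1 = x) · P(Bin(15, p) ≥ 6 − x), with X1 ~ Bin(16, p). This gives 0.0788 at p = 0.10 and 0.805 at p = 0.25, in line with the stated 0.1 and 80%.

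**Inputs for the selection effect.** K = 7 candidate types (Protocol 6.1). For cohort 213, K = 3, because "Phase 1 combination with cemiplimab will treat eligible subjects with melanoma, NSCLC, gastric/EGJ cancer, head and neck cancer or urothelial carcinoma" (Protocol 4.1.1): of the seven candidates, only gastric/EGJ, head and neck and urothelial have Phase 1 combination subjects. The documents do not give m, the number of pooled Phase 1 subjects per type, so it is assumed and varied. Further assumptions: a true ORR of p = 0.10 in every type, equal m, random tie-breaking, and selection on response alone.

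**Step 1: expected responders in the selected type.** With F the Bin(m, p) distribution function,

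E(S) = sum over x = 0 to m − 1 of [1 − F(x)^K].

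- K = 7, m = 1: 1 − 0.9^7 = 0.522.
- K = 7, m = 2: (1 − 0.81^7) + (1 − 0.99^7) = 0.771 + 0.068 = 0.839.

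**Step 2: pooled ORR under two-stage stopping.** At p = 0.10 the probability of stopping after stage 1 is PET = 0.5147, P(X1 = 1) = 0.3294, and E(X1; X1 ≥ 2) = 1.6 − 0.3294 = 1.2706. Since S is independent of the Phase 2 data,

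E(pooled ORR) = [0.3294 + PET · E(S)]/(16 + m) + [1.2706 + (1 − PET)(1.5 + E(S))]/(31 + m).

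- K = 7, m = 1: 0.5979/17 + 2.2517/32 = 0.0352 + 0.0704 = 10.6%.
- K = 7, m = 2: 0.7614/18 + 2.4058/33 = 0.0423 + 0.0729 = 11.5%.

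The comparator is pooling without selection on response, E(S) = 0.1m. It lies below 10% because stage 1 stopping pulls the unadjusted estimate down; Phase 2 alone averages 8.5%.

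| K | m | E(S) | Phase 1 ORR of chosen type | Pooled, fixed n = 31 | Pooled, two-stage | Two-stage, no selection on response |
|---|---|---|---|---|---|---|
| 7 | 1 | 0.52 | 52% | 11.3% | 10.6% | 8.6% |
| 7 | 2 | 0.84 | 42% | 11.9% | 11.5% | 8.8% |
| 7 | 5 | 1.49 | 30% | 12.7% | 12.8% | 9.0% |
| 7 | 8 | 2.04 | 25% | 13.2% | 13.4% | 9.2% |
| 3 | 1 | 0.27 | 27% | 10.5% | 9.4% | 8.6% |
| 3 | 2 | 0.50 | 25% | 10.9% | 10.0% | 8.8% |

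**Step 3: which rows the plan permits.** A Phase 1 dose cohort holds at most 15 subjects across all tumor types (Protocol 4.1.1). Equal same-dose counts in seven types need 7 × 2 = 14 for m = 2, but 7 × 3 = 21 for m = 3, 35 for m = 5 and 56 for m = 8. The rows with five or eight per type therefore need pooling across doses, which only the SAP wording could allow.

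**Step 4: selection on all doses, pooling at one dose.** With two same-dose and three to six other-dose subjects per type, selection on all of them and pooling of the two, simulation (400,000 runs) gives a two-stage pooled ORR of 10.5% down to 10.1%.

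**The case against.** The strongest reply is that neither document says response drives the choice. Phase 1 also yields safety, PK and pharmacodynamic data, and if the choice rests on those, this bias need not arise. Pooling is optional in both documents, the analyses are described as generally descriptive, and SAP 6.1 says results are generally summarized by dose level, which tells against cross-dose pooling. All of this stands, and it makes the point conditional. It does not remove it, because no written criterion keeps response out of the choice and no exception keeps the selecting subjects out of the pool.

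A reader might infer more than the documents support:

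- *That the Phase 2 decision is compromised.* It is not. The rule counts responders in the Phase 2 cohort, and the protocol confines pooling to a sensitivity analysis.
- *That false-positive claims reach about 20%.* If activity were claimed whenever the pooled two-sided 80% lower limit exceeded 10%, simulated rates would be 9.1%, 12.9% and 19.8% with three, five and eight subjects per type, against 4.6%, 5.9% and 8.2% without selection. Neither document contains that claim rule, and those equal counts do not fit in one dose cohort. With selection on eight per type and only two or three same-dose subjects pooled, the rate is 5.7% to 7.4%, below the 7.9% for Phase 2 alone.
- *That cohort 213 is affected like 203.* Four of the seven candidates have no Phase 1 combination subjects to pool.
- *That the third type lacks a disease rationale.* Protocol 4.2 gives a sialoglycan rationale for all nine tumor types.

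**Conclusion.** The point holds in conditional form. The plan lets the same Phase 1 subjects help select the third tumor type and then count in its pooled ORR, with no safeguard. Neither correct labelling nor dose matching alone provides one.

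For cohort 203 at a true ORR of 10%, with one or two same-dose subjects per type, the pooled two-stage ORR is 0.6 to 1.5 points above the truth and about 2 to 3 points above pooling without response-based selection. If the SAP is read to allow pooling across doses, five to eight subjects per type put it 2.8 to 3.4 points above the truth. For cohort 213 it averages 9.4% to 10.0% with one or two per type, no higher than the truth. The effect there is zero if ovarian, colorectal, pancreatic or breast is chosen.

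These figures assume response is the sole selector, equal true rates and equal counts per type. A smaller role for response shrinks them. The protocol's Phase 2-only primary analysis and the 6-of-31 rule (exact type I error 0.079) are unaffected. The larger exposure lies in the SAP, whose wording could bring the pooled estimate into the main efficacy analysis.

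**What to change.** Add to Protocol 9.2.5 and to SAP 6.1 and 6.3: *Phase 1 subjects with the third tumor type whose results informed its selection are not pooled into the ORR of cohort 203, or of cohort 213 where such subjects exist; their responses are reported separately.*

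In SAP 6.1 and 6.3, also state that any Phase 1 pooling is a sensitivity analysis limited to the same dose level and tumor type, as in Protocol 9.2.5, and that the Phase 2-only cohort is primary. It would help to record, before the choice is made, which Phase 1 data will decide the third type.

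Pooling for melanoma and NSCLC can stay as a sensitivity analysis. The cost is a sentence or two in each document and a few subjects fewer in an optional analysis.

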6.2. Preparation, Handling, Storage, and Accountability

The investigator or designee must confirm appropriate temperature conditions have been maintained during transit for all study treatment received, and any discrepancies are reported and resolved before use of the study treatment.

Only subjects consented to the study may receive study treatment, and only authorized site staff may supply or administer study treatment. All study treatment must be stored in a secure, environmentally controlled, and monitored (manual or automated) area in accordance with the labeled storage conditions with access limited to the investigator and authorized site staff.

The investigator is responsible for study treatment accountability, reconciliation, and record maintenance (ie, receipt, reconciliation, and final disposition records).

Further guidance and information for the final disposition of unused study treatments are provided in the Pharmacy Manual.

As E-602 is a large molecule, the drug product is supplied as a frozen liquid. E-602 should be handled and prepared by qualified study personnel using aseptic technique and administered through an IV infusion as described in the Pharmacy Manual. Details for the storage, handling, and preparation of E-602 will be provided in the Pharmacy Manual.

Cemiplimab (manufactured by Regeneron Pharmaceuticals, Inc.) is supplied as a solution (350 mg/7 mL) and administered via IV infusion. Cemiplimab should be prepared by qualified study personnel in accordance with the manufacturer's labeling.

6.3. Measures to Minimize Bias: Randomization and Blinding

Not applicable. This is an open-label study. No control group will be used.

6.4. Study Treatment Compliance

All study subjects will receive E-602 and cemiplimab (if assigned to a combination therapy cohort) at the study site and will receive the study treatment directly from the investigator or designee, under medical supervision. The date and time of each dose administered in the clinic will be recorded in the source documents. The dose of study treatment(s) and study subject identification will be confirmed at the time of treatment by a member of the study site staff other than the person administering the study treatment(s).

Protocol Number: PAL-E602-001

Version 8.0, 24 August 2023

6.5. Dose Modification

To mitigate treatment-related toxicities, the following dosing modifications will be made for both E-602 monotherapy and for E-602 in combination with cemiplimab. When E-602 is used in combination, cemiplimab should be administered first and E-602 administered at least 30 minutes after the cemiplimab infusion is completed. Dose modifications for combination therapy apply to both E-602 and cemiplimab, and both study treatments must be held or restarted according to recommended dose modifications in Table 2. Dosing visits should not be skipped due to dose delays.

All therapies should be permanently discontinued if the study treatment is not restarted within 12 weeks after the last dose for the following:

- treatment-related toxicity, per Dose Modification (Table 2), does not resolve to Grade 0–1
- corticosteroid dosing cannot be reduced to ≤10 mg prednisone or equivalent per day
- any non-treatment related toxicity does not permit restarting study treatment

Table 2 Dose modifications for E-602 monotherapy and combination therapy with cemiplimab

Adverse Reaction	Severity (CTCAE v5.0)	Dose Modification/ Action with study treatment
Hematologic events	Any Grade 3 except thrombocytopenia with bleeding as specified below	Withhold until adverse reaction recovers to Grade 0–1
	Grade 4 neutropenia not associated with clinical sequelae	
	Grade 4 thrombocytopenia without bleeding	
	Grade 3 thrombocytopenia with bleeding	Permanently discontinue
	Any Grade 4 unless specified above or recurrent Grade 3	
	Neutropenic fever	

≥1 week

Protocol Number: PAL-E602-001

Version 8.0, 24 August 2023

6.6. Management of Infusion Reactions

medication or Grade 4

As a biologic product, infusion reaction is possible with E-602 and/or cemiplimab. Investigators should assess infusion reactions from the start of an infusion through one hour after the end of the infusion. See Appendix 10.5 for CTCAE version 5.0 severity grading and acute clinical management guidelines.

6.7. Treatment of Overdose

For this study, any dose of E-602 administered greater than the 125% assigned dose will be considered an overdose. No specific information is available on the treatment of an overdose.

In the event of an overdose, the investigator should:

- Contact the medical monitor immediately.
- Evaluate the subject to determine, in consultation with the medical monitor, whether study treatment should be interrupted and/or delayed.
- Closely monitor the subject for any AE/SAE and laboratory abnormalities. Appropriate supportive treatment should be provided if clinically indicated.
- Document the quantity of the excess dose as well as the duration of the infusion.

Protocol Number: PAL-E602-001

Version 8.0, 24 August 2023

